#### 1 I. Executive summary

- 2
- 3 Chicago is an epicenter for asthma health disparities in the United States, with African American
- 4 children 5-11 years old bearing a disproportionate share of the burden. Gaps in implementation at
- 5 provider and patient levels contribute to these asthma disparities, with studies suggesting that
- 6 minority children are less likely than white children to be prescribed and use guideline-
- 7 recommended asthma care, respectively. Effective strategies to implement national asthma
- 8 guideline recommendations in this population are needed. As part of a Patient-Centered Outcomes
- 9 Research Institute contract (AS 1307-05420; Coordinated Healthcare Interventions for Childhood
- 10 Asthma Gaps in Outcomes [CHICAGO] Plan), we used methods in user-centered design to inform
- 11 the development of interventions to implement asthma guidelines in the ED and at home. We then
- 12 conducted a pragmatic trial to evaluate the effectiveness of ED and home-based interventions on
- 13 patient- and caregiver-centered endpoints.
- 14

#### 15 **II. Overview of the pragmatic trial**

16

17 The CHICAGO Plan was a randomized 3-arm parallel group, multi-center pragmatic trial in six

18 Emergency Departments (EDs) affiliated with public or private hospitals who served a high

19 proportion of black or Latino children in Chicago to compare: 1) an ED-only intervention 2) an

- 20 ED-plus-home intervention; and 3) Enhanced usual care. Eligibility criteria were intended to be
- clinically applicable and recruitment took place in multiple EDs serving underserved communities
- in Chicago (six Clinical Centers serving different populations of children 5-11 years presenting
- with asthma). Data collection employed validated approaches, but were also intended to minimize
- 24 participant burden
- 25

#### 26 III. Primary and secondary aims

- 27 28 Primary aim
- 29 Conduct a 3-arm multi-center pragmatic trial comparing the effectiveness of the ED-only, ED-
- 30 plus-home, and usual care strategies.
- 31

- 32 Secondary aims
  - Examine the potential for heterogeneity of treatment effects.
- Identify barriers and facilitators of successfully implementing the interventions to inform
   subsequent research to accelerate the uptake of study findings.
- 36

#### **Outcomes assessments**

37 38

Figure 1: Children ages 5 to 11 years who presented with uncontrolled asthma to the emergency 39 department (ED) were randomly allocated to one of three groups: Enhanced usual care vs. ED-40 based intervention using the CHICAGO Action Plan after Emergency department discharge 41 (CAPE) decision support and communication tool for children and caregivers (ED-only), vs. the 42 same ED-only intervention plus community health worker-led home visits at 2-3 days, 2 weeks, 1 43 month, 3 months, and 6 months after ED discharge to help implement the CAPE and reduce 44 45 environmental triggers (ED-plus-home). Outcomes were assessed at baseline (in-person prior to ED discharge), 1 month (via phone), 3 months (via phone), and 6 months (in-home or via phone; 46 time point for the primary outcome) after ED discharge. 47 48

#### 49 IV. Study population

50

51 Eligibility criteria were designed to be clinically relevant and feasible to implement in an ED

52 setting. Due to lower than expected randomizations during the first half of the recruitment period,

53 we modified the study eligibility criteria after review by an independent Data and Safety and

54 Monitoring Board, institutional IRBs (Site-specific IRB approval dates: Lurie – 9/14/2015; Rush –

55 9/8/2015; Sinai -9/10/2015; Stroger -8/18/2015; UC -9/1/2015; UIC -7/28/2015), and

56 discussions with the program officer from the Patient-Centered Outcomes Research Institute.

57 Original and revised eligibility criteria are below; to be eligible, patients needed to meet all

58 inclusion criteria and none of the exclusion criteria below.

59 60

#### **ORIGINAL ELIGIBILITY CRITERIA:**

61 Original eligibility criteria approved by prime site IRB (UIC #2014-1214) on 12/19/2014.

#### 62 Inclusion criteria (all of the following):

- 63 1. Child is 5-11 years of age (a population in whom a diagnosis of asthma is generally reliable, and in whom exacerbations are common);
- Child is presenting to the ED, urgent care center, or observation unit at a participating clinical
   center (Anne and Robert H. Lurie Children's Hospital of Chicago, Sinai Health System's
- 67 Mount Sinai Hospital, John H. Stroger Jr. Hospital of Cook County Health & Hospitals
- System, Rush University Medical Center, University of Chicago Medicine Comer Children's
   Hospital, and the University of Illinois Hospital & Health Sciences System);
- Child is treated with at least 1 dose of an inhaled or nebulized short-acting bronchodilator
   (quick-relief medication);
- 72 4. Child received systemic corticosteroids in the ED;
- 5. Child and caregiver approached at least 1 hour after receipt of the first dose of quick-relief
   medication or systemic corticosteroids, whichever occurred last;
- 75 6. Diagnosis of asthma exacerbation by treating clinician;
- 76 7. Treating ED clinician indicates the child is likely to be discharged to home;
- 8. Caregiver reports that English or Spanish is the preferred language at home.
- 78

#### 79 Exclusion criteria (none of the following):

- 1. Caregiver declines to provide informed consent, or the child declines to provide assent;
- 2. Child is discharged to a location other than home (e.g., hospital or another healthcare facility);
- 82 3. Child or another member of the child's primary household is a current or previous participant
   83 in the CHICAGO Plan;
- 4. Child is enrolled in another study involving a health-related intervention;
- 5. A CHW is already visiting the home as part of another program;
- 6. Child is expected to move out of Chicago within the next 6 months.
- 87

88

#### **REVISED ELIGIBILITY CRITERIA:**

89 Revised eligibility criteria approved by prime site IRB (UIC #2014-1214) on 7/28/2015. Revisions

90 occurred over a period of a few months across all of the other clinical centers (after local91 institutional review).

92

#### 93 Inclusion criteria (all of the following):

- Child is 5-11 years of age (a population in whom a diagnosis of asthma is generally reliable, and in whom exacerbations are common);
- Child is presenting to the ED, urgent care center, or observation unit at a participating clinical center (Anne and Robert H. Lurie Children's Hospital of Chicago, Sinai Health System's Mount Sinai Hospital, John H. Stroger Jr. Hospital of Cook County Health & Hospitals System, Rush University Medical Center, University of Chicago Medicine Comer Children's Hospital, and the University of Illinois Hospital & Health Sciences System);
- 3. Child is treated with at least 1 dose of an inhaled or nebulized short-acting bronchodilator
   (quick-relief medication);
- 4. Child received systemic corticosteroids in the ED OR the caregiver reported at least 1
  additional acute care visit for asthma in the previous 6 months (defined as an asthma-related
  ED visit or urgent care visit, or course of systemic corticosteroids);
- 106 5. Child and caregiver approached at least 1 hour after receipt of the first dose of quick-relief
- 107 medication or systemic corticosteroids, whichever occurred first;

- 108 6. Diagnosis of asthma exacerbation by treating clinician;
- 109 7. Treating ED clinician indicates the child is likely to be discharged to home;
- 110 8. Caregiver reports that English or Spanish is the preferred language at home.
- 111

#### 112 Exclusion criteria (none of the following):

- 113 1. Caregiver declines to provide informed consent, or the child declines to provide assent;
- 114 2. Child is admitted to an intensive care unit or transferred to another healthcare facility;
- 115 3. Child or another member of the child's primary household is a current or previous participant inthe CHICAGO Plan;
- 4. Child is enrolled in another study involving a health-related intervention;
- 118 5. A Community Health Worker (CHW) is already visiting the home as part of another program;
- 119 6. Child does not reside in Chicago.

### 120121 V. Interventions and comparators

122

All children who participated in the CHICAGO Plan received asthma care per their ED clinicians. 123 In addition, the CHICAGO Plan's ED Coordinator provided all participants two metered dose 124 inhaler (MDI) spacers free-of-charge and used teach-to-goal methodology (repeated rounds of 125 education and evaluation until the child achieves mastery) to educate the child and the caregiver 126 about appropriate MDI inhaler technique. Patient education regarding the MDI device was selected 127 because it is commonly used for quick-relief medications and is also the device for many inhaled 128 controller medications. Children were then randomly assigned to either of two active comparators 129 or enhanced usual care. 130

131

144

1. ED-only. Based on feedback from our stakeholders, we developed the CHICAGO Action 132 Plan after Emergency department discharge tool (CAPE; APPENDIX A1); a culturally 133 tailored and literacy-appropriate communication tool for use on ED discharge. Based on 134 the ED treating clinician's discharge instructions, a CHICAGO Plan ED Coordinator 135 utilized the CAPE to support guideline recommended asthma care on ED discharge (a 136 course of systemic corticosteroids; daily inhaled corticosteroids or other controller; as 137 needed quick-relief inhaled medication; education about the medications and appropriate 138 inhaler technique; education about asthma trigger avoidance; and a post-discharge follow-139 up appointment) and to support appropriate asthma self-management in the home. The 140 CAPE tool uses simplified language, visual learning, and options for individualization to 141 facilitate communication about discharge instructions between clinicians and the child and 142 caregiver. 143

2. ED-plus-home. Participants randomly allocated to the ED-plus-home intervention received 145 the same ED-only intervention described above but were also offered up to five home visits 146 over 6 months conducted by a CHW visits to: 1) assist in the implementation of the ED 147 discharge instructions, 2) update the asthma treatment plan with input from the patient's 148 ambulatory clinician utilizing the CAPE tool called the Asthma Home Plan (APPENDIX 149 A2), 3) develop a plan to manage asthma during school hours (e.g., access to quick-relief 150 medications, action plan in case of respiratory difficulty), and 4) develop a specific and 151 feasible plan to reduce environmental triggers at home (e.g., environmental tobacco smoke, 152 roach, mice). Home visits were scheduled for 60 to 90 minutes, and occurred 153

approximately at 2-3 days, 2 weeks (14 days), 1 month (30 days), 3 month (90 days), and 6 154 months (180 days) after ED discharge. 155

- 3. Enhanced usual care. Based on stakeholder feedback, we modified usual care so that 157 children in the "usual care" group also received teaching about appropriate MDI technique 158 using teach-to-goal methodology and two MDI spacers free-of-charge, as well as doorknob 159 hangers depicting facts about asthma unrelated to the study interventions. We therefore 160 refer to this group as "Enhanced usual care." To describe usual care at each site, the site 161 project manager conducted chart abstractions (masked to treatment assignment). Site 162 project managers were to complete chart abstractions within 3 business days of enrolling 163 the participant in the study. 164
- 165

#### 166 VI. Randomization

167

168 Randomization occurred at the patient level, with permuted block sizes stratified by site and race

169 (black vs. non-black). Based on data from the Clinical Centers, we expected about 70% of enrolled

170 participants to be black, 23% to be white, and that the remainder would be mostly Asian. Of the

- 171 planned enrollment of 640 children, we expected 15% to be Hispanic/Latino. Stratification by race
- for the purposes of randomization was "Black" (those who selected Black or African American,
- includes multi-race if at least one race was Black or African American) vs. "non-Black" (American
   Indian/Alaskan Native, Asian, Native Hawaiian or other Pacific Islander, white, and multi-race if
- Indian/Alaskan Native, Asian, Native Hawaiian or other Pacific Islander, white, and mulnone are Black or African American).
- 176

The CHICAGO Plan Research Electronic Data Capture (REDCap) system for study personnel
 (available 24 hours x7 days/week) provided the random treatment assignment: ED-only, ED-plus-

- 179 home, or Enhanced usual care.
- 180

#### 181 VII. Data collection

182

A. Screening and enrollment (registration) into the study (in person; ~40 minutes). The ED 183 coordinator, a member of the research team, at each Clinical Center screened patients in the ED, 184 185 Urgent Care, or Observation Unit after treatment initiation for asthma exacerbation and before discharge. The ED coordinator obtained verbal assent from the ED clinician prior to approaching 186 the child/caregiver for informed consent. Following informed consent, the ED coordinator 187 obtained Baseline data, registered the patient in a customized, secure, on-line CHICAGO Plan 188 REDCap portal developed by the DCC, then obtained the treatment assignment (ED-only, ED-189 plus-home, or Enhanced usual care). The ED Coordinator offered to arrange the date/time of the 190

- 191 l-month follow-up visit (see below).
- 192

B. 1-month follow-up contact after discharge (telephone; ~15 minutes). Post-baseline data
collection was performed by the DCC Research Assistant, who was masked to treatment
assignment. The Research Assistant conducted a telephone interview to assess outcomes
approximately 1 month after discharge. The interview was also designed to collect / update
contact information and to promote retention in the CHICAGO Plan. The DCC Research Assistant
arranged date/time of the 3-month follow-up visit (see below), or inquired about the best time to
call again.

200

C. 3-month follow-up contact after ED discharge (telephone; ~15 minutes). The DCC Research
Assistant, masked to treatment assignment, conducted a telephone interview to assess outcomes
approximately 3 months after ED discharge. The interview was also designed to collect / update
contact information and to promote retention in the CHICAGO Plan. The DCC Research Assistant
arranged date/time of the 6-month follow-up visit (see below), or inquired about the best time to
call again.

- 207
- 208 D. 6-month follow-up contact after discharge (in person or by telephone; ~40 minutes). The DCC
- 209 Research Assistant, masked to treatment assignment, conducted a study visit in person or via
- telephone (per participant preference) to assess outcomes approximately 6 months after discharge.
- 211 The in-person visit afforded the ability to conduct an assessment of home trigger avoidance;

review inhaler technique; and assess cACT (child) and PACQLQ, which are more easily collected 212 during in-person visits. 213

- 214
- E. 12-month follow-up contact after discharge (in person or by telephone; ~40 minutes). We 215
- proposed re-assessing outcomes at 12 months to examine the durability of effects observed at 6 216
- months. Despite significant efforts, retention in the study also proved to be challenging, and 217

#### therefore the 12-month follow-up visit was discontinued at the request of PCORI in September 218

2016. 219

#### 220

#### 221 **VIII.** Outcomes

- 222
- The selection of primary outcomes was based on several criteria: 1) patient-centeredness, defined 223
- as domains identified as important by children and their caregivers; as described in our previous 224
- publications; 2) availability of validated measures in English and in Spanish that could be 225
- administered in person and by phone; 3) plausibility that such measures could be responsive to an 226
- effective intervention in the target population; and 4) limited burden (e.g., time) for study 227
- participants. On this basis, we selected two NIH Patient-Reported Outcomes Measurement 228
- Information System (PROMIS) measures as primary outcomes (1 for the child and 1 for the 229
- caregiver). Several measures were selected for secondary outcomes to address recommendations of 230
- 231 national asthma guidelines, expressed preferences of caregivers and other stakeholders, and to
- compare results of the CHICAGO Plan with previous studies. 232
- 233
- A. Primary outcomes 234

1. The change in asthma impact at 6 months compared to the baseline assessed in the ED served as 235 the primary outcome in children. In children 5 to 7 years, we assessed asthma impact using the

- 236 PROMIS Parent Proxy Short Form v1.0 – Asthma Impact 8a. In children 8 to 11 years, we used
- 237
- the PROMIS Pediatric Short Form v1.0 Asthma Impact 8a. 238
- 239
- 2. The change in Satisfaction with Participation in Social Roles at 6 months compared to the 240
- baseline assessed in the ED served as the primary outcome in the caregiver. We used the PROMIS 241 Short Form v1.0 – Satisfaction with Participation in Social Roles 4a. 242
- 243
- 244 B. Secondary outcomes
- For children: 245
- 246 1) The Childhood Asthma Control Test (cACT) at 6 months compared to the baseline assessed in the ED 247
- 2) Acute care visits at 6 months (number of all-cause urgent care visits, ED visits, 248
- hospitalizations, using electronic health records) 249
- For caregivers: 251
- 252 1) Pediatric Asthma Caregiver's Quality of Life Questionnaire (PACQLQ) at 6 months compared to the baseline assessed in the ED 253
- 2) NIH PROMIS measures for anxiety, depression, fatigue, sleep disturbance at 6 months 254 compared to the baseline assessed in the ED 255
- 256 257

- 258 Indicators of guideline-consistent asthma care provided on ED discharge:
- 1) Systemic corticosteroids prescribed for use at home (yes/no)
- 260 2) Inhaled corticosteroids or another controller medication prescribed for use at home (yes/no)
- 261 3) Quick-relief medications prescribed for use at home (yes/no)
- 262 4) Follow-up appointment scheduled (yes/no)
- 263 Child's/caregiver's self-management practices after ED discharge:
- 1) Filled prescriptions for systemic corticosteroids within 7 days of ED discharge (yes/no)
- 265 2) Filled prescription for inhaled corticosteroids or other asthma controller within 7 days of
   266 ED discharge (yes/no)
- Attendance at outpatient appointment with patient-identified asthma provider within 4
   weeks of ED discharge (yes/no)

#### 270 IX. Analysis plan

271

269

- All primary and secondary outcomes were analyzed according to the intention-to-treat principle.
- All randomized subjects were included in the primary analysis, unless subjects were terminated
- due to ineligibility. Baseline sociodemographic and clinical characteristics in the intervention and
- control groups were compared using the frequency and percentages for categorical variables and
- 276 median with inter-quartile or mean with standard error for continuous variables. For bivariate
- analyses, the pairwise comparisons between three intervention arms for the change in primary and
  some secondary outcomes from baseline to 3 or 6 months were tested by Wilcoxon rank sum test.
- The W statistic, p-value and mean rank were reported together with horizontal mirror bar plots. For
- primary outcomes, a statistical significance occurred when p-value was less than 0.0167 after
- Bonferroni correction for three pairwise comparisons (0.05/3). In addition, chi-square tests were
- also conducted for other secondary outcomes.
- 283
- To address missing data in the analyses, we checked the missing completely at random (MCAR) assumption and then employed a multiple imputation strategy. Using a logistic regression method described in Hedeker & Gibbons (2006), we found that the current outcome missingness was not statistically associated with previous observed outcomes across time. Additional characteristics comparisons between participants with and without missing primary outcomes across time was also done using Chi-square tests for categorical variables and Mann-Whitney U test for continuous
- variables. No statistical difference was observed between the two groups (i.e. with and without
- 290 variables. No statistical difference was observed between the two groups (i.e. with and without 291 missing primary outcomes). We therefore used a fully conditional specification (FCS) approach to
- impute the missing values with variables of interest in the primary analysis models for 30
- 293 imputations. The raw and imputed data had similar distributions (mean, standard deviation,
- 294 minimum and maximum values).

- 296 Since the two primary outcomes were not normally distributed and our data satisfied the MCAR
- assumption, we used generalized estimating equations (GEE) to examine the effect of intervention
- group on outcomes at 3 and at 6 months compared to that of the enhanced usual care group using
- ordinal logistic regression models; the continuous dependent variables were categorized into
- quartiles. The main predictors of the unadjusted GEE models were time (0, 1, 3, and 6 months),
- intervention group, and their interactions. In an adjusted model, we added pre-specified covariates
- 302 including, race (Black vs. non-Black), ethnicity (Latino vs. non-Latino), gender (boy vs. girl),

health insurance (Public aid vs. Other), site enrolled (sites 1 to 6), number of all-cause acute care

use in the 12 months prior to enrollment (at least one vs. none). To access the intervention effect

between groups across time, we reported our results as odds ratios (ORs for higher quartiles) of

- interactions between study group and time and their 98% confident intervals [CIs; corresponding
   to a 2-sided alpha=0.0167) to account for Bonferroni adjustments for the three pairwise
- 307 to a 2-sided alpha=0.0167) to account for Bonferroni adjustments for the three pairwise 308 comparisons.
- 309

310 In secondary analyses, we explored heterogeneity of treatment effects by adding a three-way

interaction between intervention, time, and a subgroup factor in the model described previously.

312 Pre-specified subgroup factors included race (Black vs. non-black), ethnicity (Latino vs. non-

Latino), gender (boy vs. girl), and number of all-cause acute care use in the 12 months prior to enrollment (at least one vs. none).

315

316 Power / sample size calculation. The power analyses did not incorporate adjustment for the presence of two primary outcomes. Such an adjustment is not commonly made in biomedical 317 trials, as multivariate (viz. MANOVA) analyses are not commonly conducted. The power analysis 318 for single outcomes employed the Rochon (1991) method based on Hotelling's T-squared, which 319 was adapted to a 3-group comparison by adjusting the alpha level using a Bonferroni-style 320 technique. This approach tends toward a conservative (larger) sample size. We proposed to 321 enroll and randomize 640 participants over 18 months (~200-215 for each of the 3 treatment 322 groups). Assuming evaluable data in 80% of enrolled participants (n=512) at 6 months (the time-323 point for the analyses of the primary outcomes), sample size calculations suggest ample power. 324 Our approach was based on the methods of Rochon, with a Bonferroni adjustment for 3 pair-wise 325 comparisons (2-sided  $\alpha = 0.05/3 = 0.0167$ ; enhanced usual care and two active intervention groups), 326 power 80%, 4 measurements per individual (0, 1, 3, and 6 months), within individual correlation 327 0.80, correction for within ED clustering (design effect of 2), and a coefficient of determination 328 (R2) for control of individual-level demographics = 0.15. Based on these considerations, a sample 329 size of 426 (well within the expected sample size of 512) was estimated to be sufficient for a 330 minimum detectable difference of 0.35 standard deviations (SDs) (midway between Cohen's 331 "small" (0.2 SDs) and "medium" (0.5 SDs) effect sizes) for each of the two primary continuous 332 outcomes compared pairwise across the three treatment groups. The minimum detectable 333 difference of 0.35 SDs corresponds to sufficient power to detect a T-score difference of 3.5, which 334 is approximately mid-way between estimates of the minimum important difference (MID) for 335 PROMIS T-scores (2 to 5). 336

- 337
- 338

X. Barriers and facilitators of successfully implementing the intervention (Secondary aim) 339 340 Health system interventions are often multi-component, and when they successfully improve care or 341 outcomes, it is helpful to know whether all components of the intervention were necessary for 342 success. Also, when care outcomes are not improved, it is unclear if barriers to implementation 343 (fidelity) or lack of efficacy contributed to a lack of effect. We therefore a mixed -methods 344 approach to 1) assess the fidelity of implementing the ED-only and ED-plus-home interventions; 345 and 2) conduct interviews to debrief with study staff and a convenience sample of caregivers. 346 347 348 (1) Intervention fidelity: We assessed our key performance indicators (see APPENDIX B) as 349 completed or not completed to measure the extent to which each patient received each component of the CHICAGO Plan intervention, based on their allocation to the three treatment groups. 350 351 352 (2) Focus groups: We completed debrief interviews with caregivers to better understand if they were satisfied with the content, comprehension, and relevance of the intervention material. We 353 also asked about the satisfaction with the interventions provided by the ED coordinator and CHWs, 354 and any other comments the patient or caregiver would like to offer about how to improve the 355 CHICAGO Plan. We informed the participants that their responses would be used to help 356 determine how to improve studies in the future (UIC IRB # 2017-0888). 357 358 (3) Interviews of ED Coordinators, DCC Research Assistants, and CHWs: We asked study staff 359 provide feedback about barriers and facilitators to completing study procedures (e.g., space or time 360 constraints when providing ED-based instruction; availability of participants at scheduled home 361 visit times). We informed study staff that their responses would be used to help determine how to 362 improve studies in the future (UIC IRB # 2017-0888). 363 364 365

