#### 752 APPENDIX B: Key performance indicators

753 754	For eac and pro	ch, we will monitor the % completion on a monthly basis at our Steering Committee meetings ovide these key performance metrics to the DSMB prior to the scheduled meetings.	
755			
756	A. Emergency Department (ED)-level intervention performance metrics		
757			
758 759	(1)	Randomize n children/caregivers per month per site X 15 months (hereafter referred to as participants). The per-site n values are based on historical data from each site:	
760		A. John H. Stroger Jr. Hospital of Cook County: 1.7 children/caregivers per month	
761		B. Lurie Children's Hospital of Chicago: 17.5 children/caregivers per month	
762		C. Rush University Medical Center: 3.9 children/caregivers per month	
763		D. Sinai Health System: 4.0 children/caregivers per month	
764		E. University of Chicago: 12.7 children/caregivers per month	
765 766		F. University of Illinois Hospital & Health Sciences System/University of Illinois at Chicago: 2.6 children/caregivers per month	
767	(2)	% of participants who meet study eligibility criteria	
768 769 770	(3)	% of participants who have appropriate documentation of informed consent (written informed consent and assent) Age that assent is needed varies by site, listed below (site: age for assent):	
771		A. John H. Stroger Jr. Hospital of Cook County: 7 years old	
772		B. Lurie Children's Hospital of Chicago: 12 years old	
773		C. Rush University Medical Center: 8 years old	
774		D. Sinai Health System: 8 years old	
775		E. University of Chicago: 8 years old	
776 777		F. University of Illinois Hospital & Health Sciences System/University of Illinois at Chicago: 7 years old	
778 779 780 781 782 783 784	(4)	% of participants who receive the intervention as per randomized treatment assignment: (a) for the Usual Care group, the ED coordinator provides MDI instruction and Doorknob hanger; (b) for CAPE group, ED coordinator provides MDI instructions, Doorknob hanger, and completes the CAPE with the participants prior to ED discharge; (c) for ED-plus-home group, ED coordinator provides MDI instructions, Doorknob hanger, completes the CAPE with the participants prior to ED discharge; completes the CAPE with the participants prior to ED discharge, completes the CAPE with the participants prior to ED discharge, and arranges appointment for the first home visit by the community health worker.	

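### The analysis is called intention-to-treat but omits randomized children terminated as ineligible, and the rule does not limit this to facts fixed before randomization or to a decision masked to arm.

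*Combined protocol and SAP*

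**What the plan says.** The combined protocol and SAP, section IX (Analysis plan), opens: "All primary and secondary outcomes were analyzed according to the intention-to-treat principle". The next sentence reads "All randomized subjects were included in the primary analysis, unless subjects were terminated" and gives ineligibility as the ground. Termination is not defined, and no analysis that restores these children is described.

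Section VII.A sets the order of events. Children were screened in the ED, "Urgent Care, or Observation Unit after treatment initiation for asthma exacerbation and before discharge". After consent the ED coordinator "obtained Baseline data, registered the patient in a customized, secure, on-line CHICAGO Plan" "REDCap portal developed by the DCC, then obtained the treatment assignment". Appendix B, metric (4), places the arm-specific session before the child leaves: in both CAPE arms the coordinator "completes the CAPE with the participants prior to ED discharge".

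Section IV gives two kinds of criterion on disposition. Inclusion 7, in both lists, is the treating clinician's forecast that the child will probably go home. Exclusion 2 is about what occurs: discharge to somewhere other than home in the original list, and ICU admission or transfer to another facility in the revised list.

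**The concern.** Intention-to-treat protects the comparison because membership of the analysis set is settled at assignment. Under section IX, membership can also depend on a later event and on a judgment that is not stated to be masked. Omitting an ineligible child can be defended when the disqualifying fact existed before randomization and is judged without knowledge of arm. Section IX states neither condition, so the defect is the open-ended rule, not exclusion as such. At stake are an accurate label for the analysis set and a reader's ability to confirm that the arms compared are those that randomization created.

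**Working it through.** **Passages side by side**

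1. Order of events (section VII.A and Appendix B, metric 4): screening, consent, baseline data, assignment, arm-specific session, discharge.
2. Inclusion 7 can be judged before assignment because it is a forecast. Exclusion 2 may become known only after assignment because it is an outcome.
3. A child can therefore satisfy every criterion when randomized and meet exclusion 2 later. The section IX rule, as worded, permits removal of that child. The revised list narrows this route, since ordinary ward admission at the same hospital no longer excludes, but does not close it.
4. Two statements on masking come near the point. Section V describes masked chart abstraction, for the purpose of describing usual care. Section XII.G says investigators stayed masked as far as possible. Neither is tied to ineligibility terminations.

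**Possible size**

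The plan gives no number of terminations, so there is no plan figure to reproduce. What follows is a range under assumptions.

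Inputs from section IX (Power / sample size calculation): 640 children in three arms, within-individual correlation 0.80, minimum detectable difference 0.35 SD, equivalent to 3.5 T-score points (so 1 SD = 10 points).

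Assumed: an excess fraction p = 2-8% is removed from one arm only, and those removed differ from those kept by d = 0.5-1 SD, in either direction. Arm size is 640/3 = 213, so p is 0.02 × 213 = 4 to 0.08 × 213 = 17 children.

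The arm mean shifts by p × (mean kept − mean removed), which is p × d in size.

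| Nature of the difference | Formula | Low | High | Share of 0.35 SD | T-score points |
|---|---|---|---|---|---|
| In 6-month change itself | p × d | 0.02 × 0.5 = 0.01 SD | 0.08 × 1 = 0.08 SD | 2.9% to 22.9% | 0.1 to 0.8 |
| At baseline only | (1 − 0.80) × p × d | 0.2 × 0.01 = 0.002 SD | 0.2 × 0.08 = 0.016 SD | 0.6% to 4.6% | 0.02 to 0.16 |

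In the second row, a child who differs by d at baseline is expected to differ by 0.80d at 6 months, leaving 0.2d in the change score.

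**Would keeping everyone and imputing repair it?**

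This was simulated with 213 per arm, correlation 0.80, no treatment effect, 8% removed from one arm, d = 1, 20,000 runs, a linear change score, and the 6-month value imputed from baseline using that arm's kept children.

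- Difference at baseline only: the spurious contrast is about 0.015 SD with exclusion and about 0.00 with all randomized children plus imputation.
- Difference in change: 0.080 SD with exclusion and still 0.080 SD after imputation. The kept children's relation between baseline and outcome carries no information on how the removed children changed.

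All these figures are on the SD scale. They do not carry over to the odds ratios for quartiles that section IX reports.

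**The case against.** The case on the other side is substantial.

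- *The exception is disclosed in the very next sentence.* True, so nobody is misled about who was left out. The label is still inaccurate, and the grounds for removal are still open.
- *The route through exclusion 2 is inferred.* Section IV presents the criteria as conditions of eligibility, and section VII.A puts screening first. No passage says that exclusion 2 was applied after assignment. This stands: the wording permits such removal, but the documents do not show it.
- *No passage suggests that arm affects disposition.* The CAPE is completed from the treating clinician's discharge instructions. This also stands, and removal alike across arms gives no bias.
- *The assumed sizes are small.* Even the extreme corner, 0.8 T-score points, lies below the lower end of the 2 to 5 points that the plan cites as minimum important difference. This supports a modest rating.
- *Counts belong in the results report.* Fair. The missing counts are not themselves a fault of the plan. They are requested because only they can settle the question.

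A reader might also infer more than the text supports:

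- *That the plan expected ineligible children to be randomized.* Appendix B defines its participants through "Randomize n children/caregivers per month per site X 15 months (hereafter referred to as participants" and then tracks the percentage "of participants who meet study eligibility criteria". But its closing paragraph sets a goal of 100% on every metric. That is monitoring, not expectation.
- *That home visits would uncover ineligibility more often in the ED-plus-home arm.* The home-visit elements listed in Appendix B contain no eligibility check, and no passage reports such discovery.
- *That the mid-trial change of criteria biased the arms.* Randomization was by patient within site, and the revision was adopted site by site. It changes the population studied, not the contrast between arms.

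**Conclusion.** The concern holds in a limited form and should be fixed. The label does not match the analysis set, and the rule allows a correctly randomized child to be removed for an event after assignment, by a decision not stated to be masked.

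A reader might conclude that the primary comparison is biased. The documents do not support that, because they give no number, arm, reason or timing for any termination. The bias is of unknown size and direction, is zero if removal was alike across arms, and is probably small. The 0.002-0.08 SD range rests wholly on the assumed one-arm excess and the assumed difference between removed and kept children. Confidence is medium.

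Nor do the documents compel making all randomized children the primary set. The protocol is dated 12-01-2017, after data collection ended on March 31, 2017, and section IX already reports missing-data findings. Imputation would also leave the larger case unrepaired.

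**What to change.** 1. Call the set in section IX modified intention-to-treat.
2. Limit removal to eligibility facts that existed before randomization, judged masked to arm. Keep children who met an exclusion only through an event after assignment. If this brings any child back into the set, say so.
3. Add an analysis of all randomized children in their assigned arms, with the existing models and the 30 imputations. Use all data for which valid consent exists: exclusion 1 is declined consent or assent, and Appendix B allows for instances where consent was not obtained. State how many children have no post-baseline data, because imputation from baseline cannot restore a difference in change for them.
4. Report terminations by arm, reason and timing. If they were few and balanced, this table largely settles the matter.

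The cost is a revised sentence or two in section IX, one table and one extra model run on data already held, with no new follow-up. The downsides are slight dilution from a few ineligible children and a few more imputed outcomes. No passage says that terminated children were followed, so the repair may be partial. If the all-randomized set is made primary instead, disclose this as a post hoc change.
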